Study Conduct: Patients will be treated daily for 36 weeks, returning every other week (bi-weekly) for the first 12 weeks (Weeks 2, 4, 6, 8, 10 and 12) and then monthly for the remaining 24 weeks (Weeks 16, 20, 24, 28, 32 and 36) for study assessments and dose titration as needed (see Section 7.2.2). It is anticipated that by Week 12, the majority of patients will have achieved a stable dose. For safety purposes, bi-weekly visits may continue at the PI's discretion post-Week 12 if necessary.

Patients deriving clinical benefit (defined as not meeting progressive disease criteria as *per* Appendix 16.5) and safely tolerating bomedemstat may continue to receive bomedemstat beyond Week 36, with no interruption in dosing. Such patients will return for study assessments monthly. Patients discontinuing treatment with bomedemstat should undergo End of Treatment (EoT) and End of Study (EoS) visits. After 52 weeks of treatment, eligible patients may transition to a bomedemstat extension study. If available, patients who qualify can undergo an EoT visit and transition to the bomedemstat extension study without the need for a Follow up Period/EoS visit.

Patients will be followed closely throughout the study for Adverse Events (AEs) by frequent monitoring of clinical signs and symptoms as well as safety labs. Efficacy and pharmacodynamic effects will be closely monitored by frequent hematology assessments of peripheral blood. Throughout dosing, transfusions or phlebotomy may be administered if needed in accordance with standard institutional guidelines.

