ANC, absolute neutrophil count; CBC, complete blood count; Hct, hematocrit; N/A, not applicable; Plt, platelet. ^u The first up-titration is not permitted before Week 6, and the second up-titration may occur no sooner than 6 weeks after the first up-titration (e.g., if an up-titration occurs at Week 6, the next up-titration may not occur until Week 12). Beginning at Week 16, up-titrations are permitted no more frequently than every 4 weeks from the previous up- or down-titration. Down-titrations can be made (or the current dose maintained) at any time in the best interest of the patient. ^{**} Patients requiring a dose hold should have CBC with differential monitored at least weekly for safety and to enable re-challenge as soon as platelet count returns to $\geq 100 \times 10^9/L$, if safe to do so. Re-challenge at 50% of the previous mg/d dose. ^v Upon re-challenge, all of the above rules reapply.				

Study Duration: Screening may commence up to 28 days prior to first dose. Patients will receive approximately 52 weeks of dosing in this study. Participants may be eligible to enroll in the bomedemstat extension study if the participant is safely tolerating bomedemstat and receiving clinical benefit in the opinion of the investigator. Patients will be followed for 30 days post last dose. The anticipated duration of participation in the study is expected to be approximately 60 weeks from first patient visit to last patient visit.

Study Procedures and Assessments: The procedures and assessments outlined below are also summarized in Study Visit Procedures Section 9 and the Schedule of Assessments Appendix 16.1.

Informed Consent must be provided by the patient before any study-related procedures initiate.

AEs will be assessed at every visit from time of consent through 30 days post last dose (to the EoS/ED visit).

Complete Medical History including demographics, confirmation of PV diagnosis per WHO; PV disease history; PV treatment history; and phlebotomy history.

Washout of prior cytoreductive therapy for condition under study for 2 weeks (4 weeks for interferon) prior to study drug initiation. Phlebotomy may continue as clinically indicated.

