4.2 Secondary

- Durability of reduction of hematocrit to <45% without phlebotomy
- Incidence and durability of reduction of platelet count to $\leq 450 \times 10^9/L$
- Incidence and durability of reduction of white blood cell (WBC) count to $<10 \times 10^9/L$
- Incidence of new thrombotic or major hemorrhagic events
- Incidence of achieving a reduction in spleen volume by Week 36 in patients with enlarged spleen at baseline
- Incidence of progression to post-polycythemia vera myelofibrosis (PPV-MF), MDS, or transformation to AML

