Patients will return every other week (bi-weekly) for the first 12 weeks (Weeks 2, 4, 6, 8, 10, and 12) and then monthly for the remaining 24 weeks (Weeks 16, 20, 24, 28, 32, and 36) for study assessments and dose titrations as needed (see Section 7.2.2). It is anticipated that by Week 12 the majority of patients will have achieved a stable dose. For safety purposes, bi-weekly visits may continue at the PI's discretion post-Week 12 if necessary. At Week 36 a 'qualification' assessment will be performed to determine whether the patient is deriving clinical benefit (defined as not meeting progressive disease criteria as *per* Appendix 16.5) and safely tolerating bomedemstat. Patients qualifying for continued treatment beyond Week 36 should continue bomedemstat without interruption in dosing and return for study assessments monthly. Patients discontinuing treatment with bomedemstat should undergo an End of Treatment (EoT) visit on the day of last dose or as soon as possible thereafter, and an End of Study (EoS) visit approximately 30 days post last dose.

After all ongoing patients have reached 52 weeks of treatment, eligible patients may transition to a bomedemstat extension study. If available, patients who qualify can undergo an EoT visit and transition to the bomedemstat extension study without the need for a Follow up Period/EoS visit.

Patients will be followed closely throughout the study for both AEs by frequent monitoring of clinical signs and symptoms as well as safety labs. Efficacy and PD effects will be closely monitored by frequent hematology assessments of peripheral blood. Throughout dosing,

transfusions and phlebotomy may be administered if needed in accordance with standard institutional guidelines.

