6.4 Guidelines

Patient safety is paramount. The guidelines provided below are intended to provide some consistency across sites by providing guidance to be used by the Investigator, the study staff and the patient to safeguard patient safety while maintaining data integrity. The guidelines are not

intended to supersede best clinical judgment by the Investigator. Please contact the Medical Monitor with questions or with planned/known divergences from these guidelines.

1. In general, supportive care (transfusions, administration of anti-microbials, etc.) should be maintained in accordance with institutional policy. Additionally, it is advised that:
 - a. Patients with a platelet count $\leq 10 \times 10^9/L$ (10,000/ μL) be transfused.
 - b. Patients with a hemoglobin (Hb) < 8 g/dL be transfused.
 - c. Phlebotomy be performed to maintain a hematocrit $< 45\%$.
2. Patients taking medications with the potential to induce or inhibit CYP3A4 should be monitored closely for potential effects of co-administration. The Investigator may consider more frequent monitoring of complete blood count (CBC) if clinically indicated. Strong inhibitors and inducers of CYP3A4 are prohibited while on study treatment (Appendix 16.7).
3. Cessation of bomedemstat is invariably associated with a rebound in thrombopoiesis and platelet counts may easily exceed the baseline value. When bomedemstat is discontinued, the platelet count and hematocrit should be monitored closely and an alternative cyto-reductive therapy to lower platelets and hematocrit may commence within 24-48 hours, if appropriate.

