All patients will begin dosing on Day 1 at the starting dose of 40 mg/d and be treated daily for 52 weeks. Through the use of dose titration, the dose of bomedemstat will be adjusted for each patient to that dose that provides sufficient exposure to safely inhibit the activity of LSD1 in hematopoietic cells for a fraction of the dosing cycle without resulting in Grade ≥ 1 thrombocytopenia. Given the short lifespan of a human platelet compared to a red cell, approximately 7 days *versus* approximately 120 days, patients will be dosed using the platelet count as a biomarker of the activity of bomedemstat on the inhibition of LSD1. Details on the selection and rationale for the starting dose and titration schedule can be found in Section 3.7. Dose-titration, both upward and downward, is contingent on a hematology assessment. The first up-titration is not permitted before Week 6, and the second up-titration may occur no sooner than 6 weeks after the first up-titration (*e.g.*, if an up-titration occurs at Week 6, the next up-titration may not occur until Week 12). Beginning at Week 16, up-titrations are permitted no more frequently than every 4 weeks from the previous up- or down-titration. Down-titrations can be made (or the current dose maintained) at any time in the best interest of the patient. Up-titrations will be made in increments of 5 or 10 mg/d, and down-titrations in decrements of 10 mg/day.

The hematocrit titration target expected to be associated with a clinically significant therapeutic effect is:

- A hematocrit <42%

Titration and re-challenge rules to be used for titration assessment purposes, based on evaluation of platelet, ANC and hematocrit (Hct) counts are noted below.

Table 1: Titration and Re-challenge Rules

Bomedemstat Titration and Re-challenge Rules				
Important: ANC $\geq 0.5 \times 10^9/L$ (500 neutrophils/ μL) is needed for up-titration. For ANC below this threshold, maintain or adjust the current dose in accordance with the rules below.				
Hematology Assessment		Titration and Re-challenge Rules		
Plt Count ($\times 10^9/L$)	Hct %	Titration?	Titration Rule	Re-challenge Rule [¥]
≥ 450	N/A	Up-titrate [¤]	Increase by 10 mg/d [¤]	N/A
150 – <450	42% – 45%	Up-titrate [¤]	Increase by 5 mg/d [¤]	N/A
150 – <450	<42%	Maintain dose	N/A	N/A
50 – <150	N/A	Down-titrate	Decrease by 10 mg/d	N/A
<50	N/A	HOLD DOSE	N/A	At 50% of prior dose** when platelets return to ≥ 100

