12.6 Secondary Analysis

Incidence of platelet count $\leq 450 \times 10^9/L$ will be analyzed as a proportion. Frequency and percentage of patients achieving at least one result will be counted as a reduction. Similarly, WBC $< 10 \times 10^9/L$ will be analyzed. Durability of hematocrit <45%, platelet count $\leq 450 \times 10^9/L$ and WBC $< 10 \times 10^9/L$ will be analyzed by frequency achieving at least 12, 24, 36, and 52 weeks durable responses.

New thrombotic or hemorrhagic events will be analyzed separately and combined using frequency and percentage. Each patient will be counted once per event. Reduction of spleen volume to Week 36 and Week 52 will be analyzed centrally using percent change from baseline. Change and percent change from baseline in spleen volume will be measured using a continuous measure as well. Frequency and proportion of progression will be analyzed within 36 weeks and 52 weeks. If enough events occur Kaplan-Meier estimates will be graphically displayed.

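### Section 12.6 leaves the phlebotomy-free condition out of hematocrit durability, and its 36- and 52-week frequencies partly measure length of follow-up

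*Combined protocol and SAP*

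**What the plan says.** The first-listed secondary objective (Section 4.2 and Synopsis) is "Durability of reduction of hematocrit to <45% without phlebotomy". Section 12.6 turns it into an analysis of hematocrit below 45%, with no mention of phlebotomy, grouped with platelets and WBC, and says that these "will be analyzed by frequency achieving at least 12, 24, 36, and 52 weeks durable responses". It does not say when the clock starts, what ends a response, which denominator applies, or how a patient still responding at the last assessment is handled. Section 12.5 treats dropouts as nonresponders, but only for the primary endpoint. The Kaplan-Meier sentence in 12.6 follows the progression sentence and is not tied to durability. Section 12.1 defers detailed methods to a separate SAP, which is not part of the text reviewed.

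Supportive care advice in Section 6.4 includes "Phlebotomy be performed to maintain a hematocrit" below 45%.

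On the observation window, the Synopsis says "Patients will be treated daily for 36 weeks" under Study Conduct, with continuation for patients who qualify, and "Patients will receive approximately 52 weeks of dosing in this study" under Study Duration. Section 7.2.2 has patients "be treated daily for 52 weeks". Section 5.1 says "After all ongoing patients have reached 52 weeks of treatment, eligible patients may transition to a bomedemstat extension study", while the Synopsis puts transition after 52 weeks of treatment without reference to the other patients. Section 9.4 lets post-Week 36 visits repeat while a patient qualifies, and Appendix 16.1.2 lists visits to Week 72 and beyond.

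**The concern.** There are two separate problems.

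First, the analysis and the objective define different events. A patient whose hematocrit stays below 45% because of repeated phlebotomy fails the objective but meets the 12.6 criterion. The same report could then carry two 12-week hematocrit figures under different rules: the primary endpoint, phlebotomy-free and reached by Week 36, and the 12-week durability count, with neither restriction.

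Second, a bare frequency of patients reaching a given duration mixes loss of response with end of observation. Responses that begin later have less time to be observed, so the 36- and 52-week counts fall even if no one loses response. Late onset is plausible on the protocol's own account: Section 7.2.2 gives a red cell lifespan of about 120 days (120/7 ≈ 17 weeks) and allows no up-titration before Week 6.

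**Working it through.** **Phlebotomy condition, section by section**

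| Place | Phlebotomy-free condition stated? |
|---|---|
| Synopsis and 4.2, primary and durability objectives (4.1, 4.2) | Yes |
| 12.5 Primary Analysis | Yes |
| 12.6 hematocrit durability | No |
| 12.8 Interim Analysis | Yes |

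The sections on either side of 12.6 repeat the condition, so its absence cannot safely be read as shorthand.

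**Reproducing the stated study length**

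Inputs from the Synopsis: "Screening may commence up to 28 days prior to first dose", about 52 weeks of dosing, 30 days of follow-up. 28/7 + 52 + 30/7 = 4 + 52 + 4.3 = 60.3 weeks, against about 60 weeks stated. The stated participation therefore contains 52 weeks on treatment, and the next steps use that window.

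**Longest observable duration to Week 52**

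Duration = 52 − week of first qualifying visit. Scheduled hematology starts at Week 2 (Sections 5.1 and 9.3.2).

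| Onset visit | Longest duration (weeks) | Durations reachable |
|---|---|---|
| Day 1 (baseline) | 52 | 12, 24, 36, 52 |
| Week 2 | 50 | 12, 24, 36 |
| Week 6 | 46 | 12, 24, 36 |
| Week 12 | 40 | 12, 24, 36 |
| Week 16 | 36 | 12, 24, 36 |
| Week 20 | 32 | 12, 24 |
| Week 24 | 28 | 12, 24 |

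Visit windows do not change this. Week 52 is Day 365 (+3 days) and Week 2 is Day 15 (−2 days): (368 − 13)/7 = 50.7 weeks. Drawing the Week 2 sample a further 2 days ahead of the visit, as 9.3.2 permits, gives (368 − 11)/7 = 51.0 weeks.

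The latest onset that can reach each duration is Week 40 (12 weeks), Week 28 (24 weeks), Week 16 (36 weeks) and Day 1 (52 weeks).

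**Primary-endpoint responders**

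Twelve sustained weeks by Week 36 allow onset as late as 36 − 12 = Week 24. Such a patient has at most 52 − 24 = 28 observable weeks and cannot appear in the 36- or 52-week count, even with a response that never fails.

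**Treatment past Week 52**

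A 52-week duration becomes observable for onset by Week 4 if treatment runs to Week 56, by Week 8 if to Week 60, and by Week 20 if to Week 72.

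**Illustration (assumed onsets)**

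Take 15 responders of 20, as in the worked case of Section 12.2. Assume two onsets each at Weeks 6, 8, 10 and 12, three at Week 16, and two each at Weeks 20 and 24. No one loses response and follow-up ends at Week 52. Crude counts are 15/20 at 12 weeks, 15/20 at 24, 11/20 at 36 and 0/20 at 52. Kaplan-Meier among the 15 responders stays at 100% through 36 weeks, because there are no losses. The fall from 15 to 11 to 0 is entirely end of observation.

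**The case against.** The strongest reply is that the protocol does not confine observation to Week 52. Sections 5.1 and 9.4 and Appendix 16.1.2 let some patients be treated longer, and 12.6 does not fix the clock at a post-baseline value. The entry criteria set no minimum hematocrit or WBC, require platelets only of at least 250 × 10⁹/L, and allow phlebotomy before dosing, so a patient could meet a threshold on Day 1. This stands. A reader might infer that a 52-week response can never be observed; the documents do not support that. Nor do they show that only early enrollees would be observed long enough, since 9.4 ties continuation to qualification and no accrual figures are given.

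A reader might also infer that the trial will not censor. The text supports only that the protocol states no rule, with detail deferred to a SAP. Deferral does not settle the matter, because 12.6 itself fixes the method (a frequency), the durations and the hematocrit criterion.

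In a descriptive study of about 20 patients, counts observed to reach a duration are a legitimate conservative summary if labelled so. That is why they stay in the fix, next to the number followed long enough.

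Finally, an analyst who follows the objective would apply the phlebotomy condition anyway. That may happen, so an upward bias at every duration is not established. What is established is that 12.6, followed literally, permits it.

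**Conclusion.** The point holds. The phlebotomy omission is plain on the text and affects all four hematocrit durations. Its numerical effect cannot be sized, because the documents give no on-study phlebotomy rate.

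The follow-up point holds on two assumptions: observation ends at Week 52, and the clock starts at the first post-baseline qualifying visit. The longest run is then 50 weeks (51.0 with the widest windows), onset after Week 16 cannot reach 36 weeks, and onset at Week 24 leaves 28. If the clock starts at baseline or treatment continues past Week 52, a 52-week count is possible, but it then reflects baseline status or how long each patient happened to stay on study. The 12-, 24- and 36-week durations remain observable for early enough onset, so the durability analysis as a whole is not unworkable. Primary-endpoint conclusions are unaffected.

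**What to change.** 1. Insert the phlebotomy-free condition in the 12.6 hematocrit criterion.
2. Among patients who meet the response definition, report Kaplan-Meier duration for each parameter at 12, 24 and 36 weeks, alongside the crude counts and the number followed long enough for each duration. Start the clock at the first value of the qualifying sustained period. Count loss of the threshold as an event and, for hematocrit, any phlebotomy. Censor patients still responding at their last on-treatment assessment. Count discontinuation of bomedemstat for toxicity, progression or a switch to other cytoreductive therapy as an event, with censoring as a sensitivity analysis, since censoring these patients could be informative.
3. State the qualifying period for platelets and WBC, where 12.6 accepts a single result as a reduction, and how patients already within the threshold at baseline are handled. Where response itself requires 12 sustained weeks, the 12-week Kaplan-Meier value is 100% by construction, so the crude count carries that information.
4. Replace the 52-week duration with response status at the Week 52 visit, or state that it applies only to patients followed long enough.
5. Reconcile the Synopsis (Study Conduct, Dosing, Study Duration) with Section 5.1 on treatment length and timing of transition to the extension study, because these set the observation window.

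The cost is rewording of 12.6 and the SAP. No new visits or samples are needed, and the primary endpoint already requires the phlebotomy record. With about 20 patients the Kaplan-Meier estimates will be imprecise and descriptive only.

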12.8 Interim Analysis

There is 1 planned interim analysis. Descriptive analysis for sustained reduction of Hct <45% for 12 weeks without concomitant phlebotomy will be provided to evaluate efficacy. Details will be provided in the SAP.

13 STUDY ADMINISTRATION

The names, titles, and addresses of the Investigators and study personnel are available from Sponsor.

13.1 Ethical Considerations

This research will be carried out in accordance with the protocol, US Code of Federal Regulations (CFR), GCP, 21 CFR Parts 50, 56, and 312, the ethical principles set forth in the Declaration of Helsinki, and the ICH harmonized tripartite guideline regarding GCP (E6 Consolidated Guidance, April 1996).

13.2 Participation Information Sheet/Consent Form (PISCF)

A sample PISCF document will be provided to each site. No major deviations may be made from the sample PISCF other than country- or region-specific formatting or legal requirements. Sponsor and its advisors will review the site-specific draft PISCF before it is finalized, and the final IRB/IEC-approved document must be provided to Sponsor for regulatory purposes.

The PISCF must be signed by the patient before his or her participation in the study. A copy of the PISCF must be provided to the patient. If required by local procedure a second original of the PISCF may be provided to the patient. If applicable, it will be provided in a certified translation of the local language.

An original documented PISCF must remain in each patient's study file and must be available for verification by study monitors at any time.

13.3 Institutional Review Board (IRB) and Independent Ethics Committee (IEC)

This protocol, the PISCF, relevant supporting information and all types of patient recruitment or advertisement information must be submitted to IRB/IEC for review and must be approved before the study is initiated. Any amendments to the protocol must also be approved, where necessary, by the IRB/IEC prior to implementing changes in the study.

The Investigator is responsible for keeping the IRB/IEC apprised of the progress of the study and of any changes made to the protocol as deemed appropriate, but in any case, at least once a year. The Investigator must also keep the IRB/IEC informed of any AEs, according to the IRB/IEC policy.

13.4 Study or Site Termination

The EoT date is considered to be the date of Database Lock.

If Sponsor, an Investigator, or regulatory authorities discover conditions during the study that indicate that the study or related activities at a particular site should be terminated, this action may be taken after appropriate consultation between Sponsor and the Investigator. Conditions that may warrant study or site termination include but are not limited to:

1. The incidence or severity of AEs in this or other studies indicates a potential health hazard to patients

2. Patient recruitment is unsatisfactory
3. Data recording is inaccurate or incomplete
4. Investigator(s) do not adhere to the protocol or applicable regulatory guidelines in conducting the study
5. GCP is not being maintained or adequately followed
6. Administrative reasons
7. Reasons unrelated to the study.

Study or site termination and follow-up will be performed in compliance with the conditions set forth in 21 CFR Section 312 and/or other national and local regulations, as applicable, and in compliance with the principles set forth in ICH GCPs, including ICH E6, and ethical principles established by the Declaration of Helsinki.

